**Specific Aim 1:** To determine whether varenicline pharmacotherapy is enhanced by either a nicotine replacement adjuvant (i.e., patch NRT) or extended medication duration (i.e., 24 vs. 12 weeks postquit). The effects of these pharmacotherapy strategies will be reflected in main effects for both experimental factors, and in direct comparisons of the enhanced varenicline conditions with standard 12-week varenicline-only. The primary outcome will be 52-week biochemically confirmed smoking abstinence (7-day point-prevalence).

**Specific Aim 2:** To determine the effects of the varenicline conditions on additional critical outcomes such as 23-week point prevalence and prolonged abstinence, smoking cessation milestones (abstinence, latency to lapse, and lapse-relapse latency), cost-effectiveness, withdrawal severity, and adverse events. The variables that mediate and moderate (e.g., genotype) the effects of the different pharmacotherapies will also be identified.

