### **Analytic Approach**

**Cessation:** The primary outcome (biochemically confirmed, self-reported point-prevalence abstinence at 52 weeks post-TQD) will be analyzed via two strategies. First, we will conduct factorial design analyses using logistic regression with dummy coding that examines

PROTOCOL  
“Quitting Using Intensive Treatment Study (QUITS)”  
PI: [name] and [name] ; UW-CTRI Grant:

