the main and interactive effects of the two factors. Importantly, main effects obtained with dummy coding in 2-factor designs are directly interpretable even in the presence of a significant interaction as long as the interaction effect is included in the model. Thus, main effects will reflect the effects of V+P vs. V-alone, and the effects of 24- vs. 12-week treatment duration. Interaction effects would reveal whether the magnitude of differences in effects of the levels of V treatment varies in a multiplicative manner depending on duration. While we hypothesize that we will see only main effects in this research, interactions would be interpreted via visual inspection (the highest and lowest scores for the interacting treatment combinations should be readily apparent) and via simple effects tests. Second, we will conduct analyses typical of an RCT, which use logistic regression models with dummy coding to contrast each of the three enhanced varenicline treatments (12-week V+P, 24-week V-only and 24-week V+P) with the standard V-based treatment (12-week V-only). The V-only condition will serve as the reference condition because the intent is to determine if any of the enhanced V-based treatments is superior to that condition. Covariates will include sex, race, treatment site, and level of tobacco dependence (FTND item 1). Results will be reported with and without covariate adjustment and the specific effects of sex and race on each outcome will be explored. The same analytic approach will be used for secondary abstinence analyses (e.g., point-prevalence at 6-months and prolonged abstinence). The intent-to-treat principle with the assumption of missing-smoking will be used for abstinence analyses but will be supplemented with sensitivity analyses and multiple imputation for missing data to support scientific rigor. The latter models will assume that 80% of dropouts return to smoking and that abstinence likelihood is related to baseline smoker covariates. Analyses of secondary abstinence outcomes will support scientific rigor by controlling for experiment-wise error in families of related tests. Milestones analyses will be conducted as in our prior research. For instance, latency between initial abstinence and lapsing, and latency between lapsing and relapse, will be computed with Cox proportional hazards regression/survival models.

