the latter identifies the most robust interactions amongst subpopulations of a sample (groups of participants nested within levels of another predictor, which could include either a covariate or treatment condition). Candidate moderators of treatment effects on abstinence will include tobacco dependence, contextual factors such as household smoking, and biological variables such as sex and genotype. In the logistic regression analyses moderators will be evaluated with regards to their interactions with treatment main effects and interactions.

**Cost-Effectiveness:** Cost-effectiveness of key comparison treatments will be evaluated using methods recommended by the United States Panel on Cost-Effectiveness in Health and Medicine and consistent with our prior research in this area. We will: (1) measure all costs from the societal perspective; (2) convert cost estimates to a common year; (3) use a rate of 3% to discount future outcomes and costs to present value; (4) use QALYs as the outcome metric; and (5) conduct Monte Carlo sensitivity analyses. The proposed research will cost out all intervention component combinations that reflect significant main and synergistic interaction effects. We will determine net monetary benefit (NMB), cost per quit, and incremental cost-effectiveness ratios (ICERs). The components of NMB will be the added costs of the treatments and the monetized value of the QALYs added by the treatments. Using methods described by Stapleton, we will convert the increased effectiveness of the treatments from quits to added QALYs.

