The predicted data would strongly implicate the additive effects of both 24-week duration and the P adjuvant as being necessary to achieve a marked increase in abstinence over standard V-based therapy. Of course, we might discover instead that a single treatment modification or enhancement confers as much benefit as the combination of the two components (e.g., 24-week V-only produces as much benefit as 24-week V+P). This finding would be welcome to the extent that it means that exceptionally strong results are obtained with the use of only one treatment enhancement, which would save money and perhaps reduce adverse events and burden.

**Statistical Power:** We computed power (via SAS PROC POWER) for the abstinence outcomes in Table 4, assuming  $p < .05$  and two-tailed tests. Power is .88 for the main effect for Duration (n's=625), and .97 for the main effect of Varenicline (V+P vs. V: n's=625). Moreover, power is  $> .99$  for the key hypothesis that the 24-week V+P combination will be superior to 12-weeks of V-only (n's=312). The N used clearly provides some room for error if the predicted outcomes are too sanguine. For instance, we noted above that some data suggest that the increase in abstinence seen with extended medication might be as small as 7%. The proposed N (1250) would permit detection of a 7 point difference with power = .80. Thus, the N proposed would provide good power to detect the proposed effects, and even effects that are modestly weaker, but still of public health significance.

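### The factorial analysis is specified with dummy coding, whose coefficients are simple effects on about 312 vs 312, not the averaged main effects the plan describes and powers at 625 per level

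*Combined protocol and SAP*

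**What the plan says.** The Cessation paragraph of Analytic Approach gives two strategies for the primary outcome. For the first, "we will conduct factorial design analyses using logistic regression with dummy coding that examines" the main effects and interaction of the two factors. It then asserts that "main effects obtained with dummy coding in 2-factor designs are directly interpretable even in the presence of a significant interaction", provided the interaction term is in the model, and concludes that "main effects will reflect the effects of V+P vs. V-alone, and the effects of 24- vs. 12-week treatment duration". An interaction, if found, would be explored by inspection "and via simple effects tests". The second strategy also uses dummy coding, this time explicitly to contrast each of the three enhanced arms with 12-week varenicline-only.

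The approach extends beyond the primary outcome: "The same analytic approach will be used for secondary abstinence analyses". The Cost-Effectiveness paragraph will "cost out all intervention component combinations that reflect significant main and synergistic interaction effects".

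Table 4 gives predicted rates for the four cells (312 each) and for the margins (624 each). The Statistical Power paragraph says "Power is .88 for the main effect for Duration (n's=625") and .97 for the patch main effect at the same n. The comparison of 24-week combination therapy with 12-week varenicline-only is powered separately at 312 per arm.

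**The concern.** The interpretability claim is the wrong way round for dummy coding. With 0/1 codes, including the interaction is exactly what turns each lower-order coefficient into the effect of that factor at the reference level of the other. Three consequences follow if the coefficients are read as the plan says:

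- The main-effect half of Specific Aim 1 would be answered by a simple effect labelled as a main effect, using half the sample.
- With 12-week varenicline-only as reference, the two main-effect tests would repeat two of the three contrasts in the second strategy, so the factorial analysis would add only the interaction.
- The same mislabelling would pass to the secondary abstinence outcomes and to the choice of which treatment combinations are costed.

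The instruction also conflicts with the rest of the plan: the unrestricted description of the main effects, the separate listing of simple-effects tests, the Table 4 margins, and the 625 per level in the power statement.

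**Working it through.** **Inputs.** Table 4 counts out of 312 per cell: 12-week varenicline-only 78; 12-week with patch 106; 24-week varenicline-only 100; 24-week with patch 140 (the table heads the patch column V+ML; I take it as V+P). Two-sided α = .05, from Statistical Power.

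**The plan's own power figures.** Two-proportion test with pooled variance under the null, on the Table 4 margins:

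power = Φ[(|p₁ − p₂| − 1.96·√(2p̄(1 − p̄)/n)) / √((p₁(1 − p₁) + p₂(1 − p₂))/n)]

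- Duration, 29.5% vs 38.5%, n = 625: (0.090 − 1.96 × 0.02680)/0.02668 = 1.40, power .92.
- Adjuvant, 28.5% vs 39.4%, n = 625: (0.109 − 1.96 × 0.02679)/0.02661 = 2.12, power .98.
- At n = 550 per level the results are .88 and .97, which are the stated figures.

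So the stated power rests on averaged main effects, but its values fit 550 per level rather than 625. This is a separate point, not caused by the coding. The stated figures are lower than 625 per level would give. An older sample size is a possible explanation, but that is inference.

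**What the coefficients are under 0/1 coding.** With logit(p) = b₀ + b₁·D + b₂·A + b₃·D·A, setting A = 0 gives b₁ = logit(24-week varenicline-only) − logit(12-week varenicline-only). Setting D = 0 gives b₂ = logit(12-week with patch) − logit(12-week varenicline-only). The averaged main effect of Duration is b₁ + b₃/2, and that of Adjuvant is b₂ + b₃/2.

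Cell log odds, ln(x/(312 − x)), and variances, 1/x + 1/(312 − x):

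| Cell | Log odds | Variance |
|---|---|---|
| 12 wk, varenicline-only | −1.0986 | 0.01709 |
| 12 wk, with patch | −0.6644 | 0.01429 |
| 24 wk, varenicline-only | −0.7514 | 0.01472 |
| 24 wk, with patch | −0.2059 | 0.01296 |

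**Literal 0/1 coefficients, reference 12-week varenicline-only.**

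- Duration: −0.7514 + 1.0986 = 0.347; SE = √(0.01472 + 0.01709) = 0.178; z = 1.95; power .49.
- Adjuvant: −0.6644 + 1.0986 = 0.434; SE = √(0.01429 + 0.01709) = 0.177; z = 2.45; power .69.

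**Averaged contrasts from the same model.**

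- Duration: ½[(−0.7514 − 0.2059) − (−1.0986 − 0.6644)] = 0.403; SE = ½√(0.01709 + 0.01429 + 0.01472 + 0.01296) = 0.122 (0.1215 before rounding); z = 3.32; power .91; odds ratio 1.50.
- Adjuvant: ½[(−0.6644 − 0.2059) − (−1.0986 − 0.7514)] = 0.490; same SE; z = 4.03; power .98; odds ratio 1.63.

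**Joint results by simulation from the Table 4 rates.** Both main-effect tests are significant in about .41 of trials under the literal reading and .90 under averaging. Neither is significant in about .23 and .002.

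**Other reference cells.** The plan names a reference condition only for the second strategy. If 24-week with patch were the reference in the first, the coefficients would have power .79 (Duration) and .91 (Adjuvant), with both significant in about .76 of trials and neither in about .05. Literal-coding power therefore ranges over .49 to .79 for Duration and .69 to .91 for Adjuvant, below the averaged .91 and .98 in every case.

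**Unaffected contrast.** 24-week with patch vs 12-week varenicline-only: 0.893, SE 0.173, power above .99, as stated.

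**The case against.** The strongest reply is that the intended estimand is clear and one word is wrong. The plan describes unrestricted main effects, lists simple-effects tests separately, tabulates margins, and uses 625 for main effects but 312 for the cell contrast. The title of reference 107, cited for this analysis, sets effect coding against dummy coding, which also suggests a slip. The two codings give an identical fit, so nothing is lost from the data. On Table 4 the log-odds interaction is only 0.11 (SE 0.24), so the two estimands are close and the damage is mainly to precision. The figures .49 and .69 also depend on taking 12-week varenicline-only as the reference for the first strategy.

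Much of this stands. The averaged effects are recoverable, the second strategy is untouched, and the low figures are the bottom of a range, which is why the range is shown. But the reply requires the analyst to overrule the text. The same paragraph uses dummy coding for the second strategy, where it plainly means comparison with a reference cell, and nowhere gives codes or an averaged contrast for the first. The sentence on interpretability is a false statement of method, not an omission, and it claims validity precisely where an interaction is present and the two estimands diverge most.

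**Conclusion.** The concern holds and should be corrected before analysis. As written, the first primary strategy does not yield the main effects that the plan defines and powers. If its coefficients are reported literally with 12-week varenicline-only as reference, power falls from about .91 to .49 for Duration and from .98 to .69 for Adjuvant. This assumes the Table 4 rates, 312 per cell and two-sided .05.

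The loss is conditional on the literal reading; an analyst who forms the averaged contrasts avoids it. The other half of Specific Aim 1, the effects shown "in direct comparisons of the enhanced varenicline conditions with standard 12-week varenicline-only", is not affected.

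**What to change.** - For the first strategy, and for the secondary outcomes that follow it, name one main-effect test per factor: the averaged log-odds contrast from the model with the interaction retained. Effect coding delivers it.
- State the codes and match the reporting to them. With −1/+1 codes the coefficient is half the averaged log odds ratio, so report exp(2b); with −0.5/+0.5 codes report exp(b). Printing exp(b) under −1/+1 codes would show 1.22 and 1.28 where the averaged odds ratios are 1.50 and 1.63.
- Rewrite the interpretability sentence so that it refers to effect coding.
- Keep dummy coding, with 12-week varenicline-only as reference, for the second strategy only.
- Restate main-effect power for 625 per level (about .92 and .98 on the Table 4 margins), or say which sample size the printed figures belong to.
- If a standardised risk difference is also reported, label it supplementary. This is a matter of presentation, and the correction does not depend on it.

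The cost is a few sentences in Analytic Approach and Statistical Power and one line of analysis code. Data collection, sample size, randomisation and the second strategy do not change.

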## **Assessments**

*Baseline:* These will constitute covariates for analyses (e.g., smoking dependence, heaviness, history), characterize the cohort, and capture baseline levels of potential mediators of treatment effects. They also will permit assessment of constructs that will be used to develop an optimal, patient-centered treatment algorithm. The surveys (gathered at Visit 1: Table 2; associated references provide psychometric data) will include: (1) The Smoking History Questionnaire, which provides accurate information about lifetime smoking cessation treatment history, family smoking, environmental exposure, and psychiatric history; (2) The Brief Wisconsin Smoking Dependence Motives questionnaire (Brief WISDM); (3) The Fagerstrom Test for Cigarette Dependence (FTCD); (4) Alcohol use and problems assessed with a quantity-frequency measure for the past week; (5) The Wisconsin Predicting Patients' Relapse questionnaire (WI-PREPARE) which may inform algorithm development; (6) The 5-trial Adjusting Delay Task to assess ability to delay reward; (7) interview about changes to make to quit successfully; and (8) the Depression, Anxiety and Stress Scales (DASS-21) to assess current symptoms of depression, anxiety and stress. In addition, a psychiatric history will be gathered that assesses prior diagnoses and treatment for psychiatric disorders including substance use (as per). Blood will be drawn (about 2 tablespoons) for DNA extraction and genotyping as in prior UW-CTRI RCTs and for serum cotinine analysis. Breath carbon monoxide will be assessed.

*DNA assessments.* Samples for DNA analysis will only be taken from those providing consent for this. As outlined in the Biological Samples protocol supplement, blood will be drawn for samples of DNA for genetics, DNA for methylation (Madison site only), and RNA(Madison site only). DNA for genetics will be extracted by the UW Biotechnology Center. All three samples will be relabeled at the UW Biotechnology Center with DNA IDs/ barcodes, which allows connecting additional data secured from participants at later visits but does not contain HIPAA identifiers that can be connected back to the study. Samples will be stored at both the UW Biotech Center (DNA for genetics @-80°C) and CTRI Madison (DNA for methylation and RNA @-20°C) until shipped in batches to Washington University. Banking will occur at Washington University in St.

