**Table 2. Schedule of Study Activities**

	Pre-Cessation	Treatment Phase						Phone Follow-up				
		V1	C1	V2	V3	C2	C3	C4	C5	C6 	C7	C8 
Week	Orientation	Wk - 2	-1	TQD	2	4	8	11	17	23	39	52
Screening & Informed consent	X											
Randomization	X											
Pre-cessation counseling		X	X									
Cessation counseling				X	X	X	X					
Exhaled CO	X	X		X	X					X 		X 
Short questionnaire on CO exposure	X	X		X	X					X 		X 
Smoking status	X	X	X	X	X	X	X	X	X	X	X	X
Blood sample for DNA/RNA and cotinine		X										
Non-cigarette nicotine use	X	X		X		X	X			X		X
Baseline questionnaires	X	X										
IVR assessments	X	X	X	X	X							
Treatment mechanisms assessment 		X	X	X	X	X	X	X	X	X	X	X
Medication provision		X		X			X					
Medication use assessment			X	X	X	X	X	X	X	X	X 	
Adverse events			X	X	X	X	X	X	X	X	X	X

If participants claim abstinence during this assessment call, they will be invited to an in-person visit to provide biochemical verification of abstinence (CO assessment).

Treatment mechanisms include withdrawal, affect, fatigue, cigarette liking/effects, stressors, cue exposure, motivation, and self-efficacy.

Timeline follow back only

week post-quit). Per our intention-to-treat data analysis plan, any randomized smoker who does not provide biochemically confirmed evidence of abstinence will be counted as a smoker; multiple imputation also will be performed in secondary analyses to further enhance scientific rigor. A daily smoking calendar will permit determination of lapse/relapse latencies for survival and milestones analyses. In order to enhance *scientific transparency*, we will post all assessment instruments and, ultimately, de-identified data, online (e.g., the UW-CTRI website; average of 7,000 hits/month over last year from 17,387 visitors), so that other researchers can use our de-identified data and instruments (see detail in Data Sharing Plan).

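### The adjusted primary models use only the four covariates that match the stratification factors; a few baseline predictors already being collected would add a small, nearly free gain in precision

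*Combined protocol and SAP*

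**What the plan says.** The Cessation paragraph of Analytic Approach sets out two logistic regression strategies for the primary outcome: a factorial model, and contrasts of each of the three enhanced arms with 12-week varenicline alone. On adjustment it says: "Covariates will include sex, race, treatment site, and level of tobacco dependence (FTND item 1". Results are to be given both adjusted and unadjusted. Recruitment & Study Entry names sex, site, dependence and race as the stratification factors, so the covariates match them one for one. The protocol does not say how dependence was graded for stratification.

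The Baseline paragraph of Assessments says of the baseline measures: "These will constitute covariates for analyses (e.g., smoking dependence, heaviness, history". The list that follows includes a smoking history questionnaire, the Brief WISDM, the full FTCD and "The Wisconsin Predicting Patients' Relapse questionnaire (WI-PREPARE) which may inform algorithm development". Exhaled CO is also measured. The same paragraph gives these measures other purposes: describing the cohort, recording baseline levels of mediators, and building a treatment algorithm.

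The multiple-imputation models in Analytic Approach assume that "abstinence likelihood is related to baseline smoker covariates".

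**The concern.** The plan treats baseline smoking characteristics as prognostic when it imputes missing abstinence, but the adjusted primary models carry only one dependence item and three demographic or site factors. Smoking heaviness, history, the rest of the FTCD and the relapse-risk questionnaire do not appear among the named covariates, and the plan does not comment on leaving them out.

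In a randomized comparison, adjusting for a baseline variable that predicts the outcome raises the power of the treatment test. Two of the three arm contrasts have room for this: 12-week varenicline plus patch, and 24-week varenicline alone, each against standard treatment. The main effects and the 24-week combination contrast are already well powered at the Table 4 rates and have little to gain.

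The covariate sentence also does not say that its list is closed. As written, it does not rule out choosing further covariates after outcomes are known.

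**Working it through.** **Inputs.** Predicted 52-week abstinence (Table 4): 25.0% for 12-week V-only, 34.0% for 12-week V+P, 32.0% for 24-week V-only, 44.9% for 24-week V+P. The Statistical Power paragraph gives alpha 0.05 with "two-tailed tests", and the sample size for an arm contrast: "24-week V+P combination will be superior to 12-weeks of V-only (n's=312". There is no reduction for dropout, because "any randomized smoker who does not provide biochemically confirmed evidence of abstinence will be counted as a smoker".

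**Formula.** Power = Φ{(|p2 − p1| − 1.96·SE0)/SE1}, where SE0 = √[2·p̄(1 − p̄)/n], SE1 = √[(p1(1 − p1) + p2(1 − p2))/n] and p̄ is the mean of the two rates.

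**Plan's own figure first.** 44.9% vs 25%, n = 312: SE0 = 0.0382, SE1 = 0.0373, power = Φ{(0.199 − 0.0748)/0.0373} = Φ(3.33) = 0.9996. The plan states above .99, so this agrees. At 625 per level the same formula gives 0.98 for the Adjuvant main effect (stated .97) and 0.92 for Duration (stated .88). The Duration gap is a separate matter and does not affect this point.

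**The two contrasts for which the plan states no power.**
- 34% vs 25%: SE0 = 0.03651, SE1 = 0.03633, power = Φ{(0.09 − 0.07157)/0.03633} = Φ(0.507) = 0.694.
- 32% vs 25%: SE0 = 0.03614, SE1 = 0.03603, power = Φ{(0.07 − 0.07084)/0.03603} = Φ(−0.023) = 0.491.

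With a continuity correction or Fisher's exact test, these fall to about 0.66 and 0.455.

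**Effect of adding a predictor.** The documents give no prognostic strength, so it is assumed over a range. Logistic models were simulated with 312 per arm and one standardized baseline score, 4,000 runs per setting. Each setting was analysed with and without the score on the same simulated data.

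| Assumed AUC of the score | 34% vs 25%: unadjusted → adjusted | 32% vs 25%: unadjusted → adjusted |
|---|---|---|
| 0.58 | 0.706 → 0.717 | 0.496 → 0.501 |
| 0.63 | 0.690 → 0.715 | 0.490 → 0.509 |
| 0.68 | 0.701 → 0.739 | 0.488 → 0.516 |
| 0.74 | 0.706 → 0.779 | 0.492 → 0.561 |

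A single simulated power has a standard error of about √(0.7 × 0.3/4000) = 0.007. This explains why the unadjusted column scatters around 0.694.

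A second simulation of the first contrast (3,000 runs) gave 0.680 → 0.688 at R² = 0.016, 0.683 → 0.705 at 0.044, 0.704 → 0.743 at 0.092 and 0.682 → 0.777 at 0.194. A cruder approximation that multiplies the variance by 1 − R² passes 80% only for the first contrast and only at an assumed R² of 0.25 (0.81). The second contrast then stands at 0.61.

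These strengths must be read as what the new measures add beyond the four covariates already in the model. FTND item 1 already carries part of the dependence signal.

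**Model size.** Table 4 implies 184 + 240 = 424 abstinent participants, so two or three more terms are easily supported.

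**The case against.** Three stronger readings are tempting, and the documents do not support them.

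1. **That the plan contradicts itself.** The Assessments sentence speaks of analyses in general and names no model. Baseline variables do appear elsewhere: in the imputation models, in the mediation models, and as candidate moderators. A general statement followed by a specific list for one analysis is ordinary drafting.
2. **That the covariate list explains the low power.** The 0.69 and 0.49 come from 312 per arm and the predicted rates. They would be nearly the same under any realistic covariate set.
3. **That the omitted measures are all taken before randomization and held for everyone.** Randomization takes place at Orientation. The Assessments section places the surveys at Visit 1, which comes later; Recruitment & Study Entry mentions baseline assessments at Orientation, and Table 2 marks both. Anyone randomized who misses Visit 1 could lack whole questionnaires.

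The strongest defence of the plan is that adjusting for the stratification factors is standard, pre-specified and sufficient. That defence is sound for keeping the four. It also rules out simply replacing FTND item 1 with the FTCD total, since item 1 may be the stratifier. It does not show that adding other predictors is unwise.

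Two further objections carry limited weight. Adding predictors to a logistic model changes the conditional odds ratio being estimated, but the existing four-covariate model does this too, and the unadjusted result is reported alongside. Visit 1 scores taken after randomization are still usable under double-blind assignment, provided they are recorded before the first dose.

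**Conclusion.** The point stands as a minor, optional improvement. The adjusted primary models use a sound but minimal covariate set and pass over baseline predictors the trial already collects.

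The expected benefit is about 1 to 4 points of power for modest predictors (0.5 to 3.7 in the table) and about 7 for a strong one (9.5 at the top of the second simulation). It applies to the two contrasts that start at 0.69 and 0.49. Neither reaches 80% in either simulation, so better adjustment does not remedy the power of those contrasts.

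These figures rest on the Table 4 rates, 312 per arm, two-sided 0.05 without a multiplicity adjustment, and an assumed prognostic strength that the documents do not give. If the added measures contribute little beyond FTND item 1, the gain is close to nil.

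**What to change.** In Analytic Approach, before unblinding:

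- Keep sex, race, site and the dependence measure actually used for stratification, and state what that measure was.
- Add a short closed list of baseline predictors as continuous terms, for example the FTCD total or cigarettes per day, plus one WI-PREPARE score whose scoring is defined in the plan.
- Use only values recorded before the first study medication.
- Pre-specify simple imputation or a missing-value indicator for these terms, so that every randomized participant, including anyone who misses Visit 1, stays in the intention-to-treat model.
- Continue to report the unadjusted result.
- In Assessments, say which baseline measures enter which analysis.

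The cost is a change of wording, with no new data collection. The downsides are two or three extra parameters against about 424 expected events, some imputation of baseline values (possibly whole questionnaires for those who miss Visit 1), and a slightly different conditional odds ratio. Cigarettes per day should be the easiest to obtain for everyone, because eligibility depends on it.

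### The single 80%-relapse imputation does not say how it applies by arm; if the same figure is used in each arm, it cannot test differential relapse among dropouts

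*Combined protocol and SAP*

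**What the plan says.** The primary rule is in the Smoking Outcome Measures text that continues after Table 2: "any randomized smoker who does not provide biochemically confirmed evidence of abstinence will be counted as a smoker". The same paragraph adds that "multiple imputation also will be performed in secondary analyses to further enhance scientific rigor". The Cessation paragraph of the Analytic Approach section repeats the rule and says that it will be "supplemented with sensitivity analyses and multiple imputation for missing data to support scientific rigor". It then gives the only detail on the imputation: "The latter models will assume that 80% of dropouts return to smoking and that abstinence likelihood is related to baseline smoker covariates".

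The plan gives one relapse figure and names one class of predictor. It gives no arm-specific figure, no range and no tipping point. It does not say whether treatment arm, or smoking status recorded after baseline, is in the imputation model. The further sensitivity analyses are promised but not described. The effect scale is the odds ratio: "we will conduct factorial design analyses using logistic regression with dummy coding". No dropout rate is stated.

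**The concern.** Missing=smoking assumes that every dropout relapses, whatever the arm. A useful supplementary analysis should relax the part of that assumption that can bias a treatment contrast, namely that relapse among dropouts is the same in the arms being compared. Changing a common 100% to a common 80% changes the level of abstinence in both arms but leaves that part in place. Close agreement between the two analyses would then say little about robustness.

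Reasons for leaving could differ by arm. The note to Table 3 allows medication to be stopped or reduced for adverse events, and the arms differ in both the number of active agents and the length of active treatment. The trial also collects better information than the predictors named for the imputation: smoking status by phone at Weeks 4, 8, 11, 17, 23 and 39, and a daily smoking calendar.

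**Working it through.** **Plan's own figures.** The documents report no imputation result and no dropout rate, so there is nothing to reproduce on this exact point. The nearest stated figure is the Duration power of .88 with 625 per level. A pooled two-proportion calculation gives .92 at 625 and .884 at 550 per level. That is a separate matter and nothing below depends on it.

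**Inputs.** Table 4 rates, taken as the missing=smoking rates:
- Duration: 29.5% (12 weeks) and 38.5% (24 weeks), 624 per level.
- Standard 12-week varenicline-only 25.0% and 24-week combination 44.9%, 312 each.
- Two-sided .05, from the Statistical Power paragraph.
- Assumed: dropout of 10-30%, and the arm-specific relapse values.

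**Formula.** With dropout d, completer abstinence a and dropout abstinence q, the arm rate is (1-d)a + qd. Missing=smoking sets q=0; the stated imputation, read as common to the arms, sets q=.20. The change in risk difference (24 minus 12 weeks) is q24·d24 - q12·d12.

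**1. Common 80%, equal dropout.** At d=.20 both levels gain .20×.20 = 4.0 points: 42.5 - 33.5 = 9.0, as before. The combination contrast stays at 19.9. A 400-trial simulation with covariate-dependent imputation and 25% dropout gave mean Duration differences of 8.81 (missing=smoking) and 8.82 (imputation). The gap had an SD of about 0.6 points, so the equality holds on average and not in each trial.

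**2. Odds ratio.** Missing=smoking: (.385/.615)/(.295/.705) = 1.496. Common 80%, d=.20: (.425/.575)/(.335/.665) = 1.467. The combination odds ratio goes from 2.445 to 2.343.

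**3. Common 80%, unequal dropout.** The shift is .20×(d24 - d12). A 5-point gap gives 1 point. Dropout of 20% (12 weeks) and 30% (24 weeks) gives 11.0 points; the reverse gives 7.0.

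**4. Relapse differing by arm.** Take 90% at 24 weeks and 70% at 12 weeks, still averaging 80% (q = .10 and .30). The p-values are from pooled two-proportion tests and ignore imputation variance.

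| Dropout | 12 weeks | 24 weeks | Difference | p |
|---|---|---|---|---|
| Missing=smoking | 29.5% | 38.5% | 9.0 | .0008 |
| 10% | 32.5% | 39.5% | 7.0 | .01 |
| 20% | 35.5% | 40.5% | 5.0 | .07 |
| 30% | 38.5% | 41.5% | 3.0 | .28 |

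For the 20% row, SE = √(.38×.62×2/624) = 2.75 points and z = 5.0/2.75 = 1.82. A common 80% at 20% dropout would show 9.0 points, p=.001. Reversing the relapse pattern at 20% dropout gives 13.0 points.

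**5. Tipping point for Duration.** With average relapse held at 80%, significance is lost when the relapse gap exceeds (9.0 - 1.96×SE)/d. At 20% dropout this is (9.0 - 5.39)/.20, about 18 points. At 30% it is (9.0 - 5.44)/.30, about 12. At 10% it is (9.0 - 5.33)/.10, about 37.

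**6. Key combination contrast.** At 20% dropout and 90% against 70% relapse: 46.9 - 31.0 = 15.9 points, SE = √(.3895×.6105×2/312) = 3.90 points, z about 4.1.

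**7. The other reading of the sentence.** Suppose 80% is imposed on the pooled dropouts with arm in the model, so that dropout odds are proportional to completer odds. At 20% dropout q is .163 and .237, and Duration becomes 9.0 + .20×7.4 = 10.5 points. At 30% (.159 and .241) it is 11.5.

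**The case against.** A reader might infer that the plan fixes 80% relapse in every arm, so that the imputation must reproduce the primary result and tests nothing. The documents do not support that much.

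- The text gives an overall 80% and is silent on arm. It does not say that only baseline covariates are used. Step 7 shows that another permissible reading gives a different answer, so the equality in step 1 is conditional.
- The planned estimate is an odds ratio, and that does change, though too little to be a stress test.
- The imputation does respond to unequal dropout (step 3). What it leaves untested, under a common 80%, is unequal relapse.
- Separate sensitivity analyses are promised. They are undescribed, so it cannot be said that differential relapse will go unexamined, only that nothing specified examines it.
- The primary rule covers everyone without biochemical confirmation, while the 80% covers dropouts. The plan does not say that these groups coincide, and the algebra treats them as one.

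The choice of contrast also matters. For 24- against 12-week varenicline alone, the Table 4 counts (100/312 and 78/312) give p=.051 under missing=smoking, so there is no significance to lose. The plan's key combination contrast survives the 90%/70% scenario. These points narrow the concern without removing it: the sentence is ambiguous on arm, and no stated analysis varies relapse by arm.

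**Conclusion.** The point holds in conditional form. The imputation is under-specified on arm and on post-baseline smoking status. If one 80% is applied in each arm, it cannot test differential relapse among dropouts: the expected risk difference is unchanged under equal dropout and moves about 1 point per 5-point dropout gap. The exposed result is Duration, which at the predicted rates falls from 9.0 points to 7.0, 5.0 or 3.0 at 10%, 20% or 30% dropout under 90% against 70% relapse. It loses significance in the last two cases. The combination contrast stays significant at about 16 points at 20% dropout.

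These sizes rest on assumed dropout, an assumed 20-point relapse gap, Table 4 read as missing=smoking rates, and tests that ignore imputation variance. They do not show that relapse will differ by arm, or that the primary analysis is wrong. This is an inexpensive improvement to a secondary analysis.

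**What to change.** Keep missing=smoking as primary. In the Analytic Approach section:

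1. State whether the 80% applies within each arm or to pooled dropouts, and whether dropouts means those lost to follow-up or everyone unconfirmed.
2. Impute from arm, the stratification factors, baseline covariates and observed Week 4-39 smoking status.
3. Define the promised sensitivity analyses as a grid of arm-specific relapse fractions (for example 60-100% in each arm). For each primary contrast, report the tipping point at which significance is lost.

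The cost is revised wording and extra analysis of data already collected. The downside is that work, and possibly a less favourable robustness statement, most likely for Duration.
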